A proposed randomized clinical trial of the effectiveness of a new breastfeeding- supportive texting program designed specifically for African-American/Black expectant women, as compared to a national maternal health texting program, on rates of exclusive breastfeeding at 2months; Short title: TOPS – Texting to Promote Breastfeeding).

XXXXXXXXXXXXXX

NCT06375655

01/19/2024

Objectives

Specific Aims

- 1. Demonstrate the feasibility and acceptability of a scaled-up program to deliver Team2BF text messages to AA/B expectant women considering breastfeeding.
- 2. Compare breastfeeding outcomes in the group receiving Team2BF with rates among those receiving Bright By Text.
- 3. Compare breastfeeding related knowledge and self-efficacy and social support as moderators of the relationship between the texting intervention and breastfeeding outcomes. (Exploratory aim)
- 4. Compare other key health outcomes (appointment attendance and vaccine receipt and book reading to infant) between the groups to verify that a focus on breastfeeding enhances rather than detracts from general maternal-infant health outcomes. (Exploratory aim)

Study Hypotheses

- Participants will find the Team2BF intervention acceptable as measured by >90%
 continuation, by >75% top score helpfulness of messages for breastfeeding and >75%
 endorsement of friend and family referral.
- 2. Participants receiving Team2BF will have significantly higher exclusive breastfeeding rates at 2 months as compared to participants receiving Bright By Text.
- 3. Breastfeeding knowledge, perceived social support for exclusive breastfeeding and self-efficacy will positively moderate the relationship between texting and breastfeeding outcomes, with those in the Team2BF group demonstrating a significantly greater increase in these domains with time as compared to the Bright By Text group.
- 4. Participants in both groups will have >75% rates of attendance among mothers at the (2-6 weeks) postpartum obstetrical visit and >75% rates of attendance and vaccine receipt for infants at the 2 month (6-12 weeks) well care visit.

Background

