The study intervention is texting of health information from 28 weeks gestation or from time of enrollment (24-34 weeks) through one year postnatally. Participants will be block randomized to either Bright By Text or Team2BF. Blocks will be by CenteringPregnancy group for those in this program and in sequential blocks of the same number of participants for those in individual obstetrical care.

Those randomized to Bright By Text begin receiving texts as soon as they sign up, and those randomized to Team2BF begin receiving texts at 28 weeks or at the time of enrollment if after 28 weeks.

Bright By Text sends messages total from the first trimester through eight years postpartum, with 2-4 messages per week about a wide range of maternal and child health topics as outlined on their website; there are in total 8 messages about breastfeeding from the prenatal period to 4 months postpartum. Team 2BF includes 3-4 breastfeeding-supportive messages per time

interval, sent weekly from 28 weeks gestation through delivery, daily through 2 weeks postpartum, weekly from 2 to 10 weeks, and then monthly to one year. Other maternal health topics are not addressed.

We are not able to collect user interactions with the SMS system (were texts read or not, was message link clicked or not) within the TEAM2BF REDCap/Twilio system; Bright By Text does have ability to collect user interactions but there is no plan to collect this information for the research and no ability for the study team to receive or access it. For TEAM2BF, participants can text STOP ALL or STOP SO MANY (to receive only one message per time point [by week prenatally or by day postpartum]) and for Bright By Text, participants can text STOP at any time to discontinue receiving texts. At the point of any unsubscribe, and at the 6 months postpartum time point, the participant will be invited by text to participate in a 10-15 minute interview about their experience The interview will be audio recorded and the transcript destroyed once call notes are verified against the recording.

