| | Breastfeeding Knowledge Quiz (4 | | | | |
| | questions – answers follow) | | | | |
| | Breastfeeding Self-Efficacy Scale (14 | | | | |
| | items) | | | | |
| One week after | Infant Feeding Information-what milk is | 2 minutes | | | |
| delivery (PP) | baby drinking? | | | | |
| One month PP | Infant Feeding Information | 2 minutes | | | |
| Two months PP | Infant Feeding Information | 15 minutes | | | |
| | Breastfeeding Knowledge Quiz | | | | |
| | Breastfeeding Self-Efficacy Scale | | | | |
| | Breastfeeding Social Support Scale (16 | | | | |
| | items) | | | | |
| | Maternal Satisfaction (6 questions) | | | | |
| Three months PP | Infant Feeding Information | 3-4 minutes | | | |
| | Healthy Development (1 question) | | | | |
| | Maternal Satisfaction (6 questions) | | | | |
| Six months PP | Infant Feeding Information | 8-17 minutes | | | |
| | Healthy Development | | | | |
| | Maternal Satisfaction (6 questions) | | | | |
| | Study Thank you Survey | | | | |

Data to be Collected for your study

Outcome Measures

Aim #1 - Acceptability

Receipt of messages measures acceptability because participants can easily end messaging; if at least 90% of Team2BF participants continue receipt this will indicate acceptability of the intervention. This outcome will be enhanced by asking (a) a single 4 point Likert-scaled question

about the helpfulness of the texts for breastfeeding and (b) whether the participant would or would not refer a friend or family member to Team2BF.

Aim #2 – Breastfeeding Outcomes

The main outcome will be exclusive breastfeeding at 2 months because this is a meaningful milestone toward the public health goal of 6 months exclusive breastfeeding. We will assess partial and exclusive breastfeeding at hospital discharge and at 1, 2, 3 and 6 months post delivery using the World Health Organization definitions for exclusive and partial breastfeeding. We will also assess timing of discontinuation of breastfeeding if this occurs.

Aim #3 – Moderators of Breastfeeding Outcomes (Exploratory aim)

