By measuring breastfeeding knowledge at enrollment and again at 2 months we will assess for change in knowledge and for relationship to the main breastfeeding outcome. By measuring self-efficacy at enrollment and 2 months we will assess for changes in self-efficacy and relationship to the main breastfeeding outcome. We will assess perceived social support for exclusive breastfeeding at 2 months to compare those who did and did not achieve this goal.

Aim #4 – Non-breastfeeding Health Outcomes (Exploratory aim)

We will compare other key health outcomes between the groups that have been documented as relevant Bright By Text outcomes, as a direct Bright By Text outcome and a proxy to verify that a focus on breastfeeding enhances rather than detracts from general maternal-infant health outcomes. Attendance at the maternal postpartum check and attendance at the infant 2, 4 and 6 months well care appointments, including whether age-appropriate vaccines were received, will be assessed, as well as a measure of literacy (number of days per week reading books to baby).

Management of surveys – Generally participants will complete the enrollment timepoint surveys electronically, but if their phone is not able to photograph the QR codes that lead to the enrollment surveys, these will be administered on paper. The documents will be maintained on and transferred on the person of the study team member to the CCHP (Center for Child Health Policy) Office MCCO 650. The surveys will be kept in a locked cabinet with study team member access only, and after entry into REDCap will be retained until data analysis is complete.

Data Analysis Plan

Populations of each group will be compared using descriptive statistics (means and ranges, percents and frequencies). The main outcome of breastfeeding exclusively at 2 months will be compared between the two arms (texting groups) controlling for factors known to impact breastfeeding rates, as well as site of enrollment.

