The privacy of participants will be protected. The consent process will occur in a private space or virtually where the potential participant can protect their own privacy. All interventions occur virtually on a personal phone, so participants are not exposed to others.

Potential Benefit to Research Participants

There are no direct benefits guaranteed to participants. Participants may benefit if the TEAM2BF messaging helps them with their breastfeeding and may benefit if Bright By Text

increases their wellness, but this cannot be guaranteed. We hope the information gained will help future women, their families and their health providers with breastfeeding and ultimately reduce racial inequities in breastfeeding.

Withdrawal of Research Participants

All participants can text STOP to unsubscribe at any point and withdraw themselves from the research and from each of the texting programs. A participant would be withdrawn is if there is any abuse of the texting system with receipt of inappropriate or profane messages. Mother participants who deliver prior to 36 weeks (35 and 6/7 weeks or before) will be exited from the study since the postnatal messaging is not tuned for prematurity.

Alternatives to Participation

The alternative to participation is simply not to participate. The research is not a substitute for clinical care.

Costs to Research Participants

There could be a cost for the texting for participants depending on their phone plan. The study team cannot be responsible for these costs.

Research Participant Compensation

At enrollment, at 1 week postpartum and at 1, 2, 3 and 6 months we will give \$25 gift card and a tangible gift (diapers+wipes or onesies).

Provisions to Monitor the Data to Ensure the Safety of Research Participants

The PI and research coordinator will meet at least every other week to review for adherence to protocol, trouble shooting, and any events. We will not convene a DSMB.

Drugs or Devices

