Participants will use their own smartphones for the study. The smartphone is a device but it is not being studied. The text messages are being studied. Given the definition of software as a medical device (The term "Software as a Medical Device" (SaMD) is defined as software intended to be used for one or more medical purposes that perform these purposes without being part of a hardware medical device. Reference- https://www.fda.gov/medical-devices/digitalhealth-center-excellence/software-medical-device-samd), the text messaging does not appear to be SaMD because it is not being used to treat, diagnose, cure, mitigate or manage a condition or disease. There are no drugs involved in this study.

Additional Information

The program that is used for the TEAM2BF texting is currently Twilio via REDCap. Twilio, a third-party web service, allows SMS text messages to be sent via REDCap Links within the messages go to free content – most content is publicly available, and for those PDFs that are not publicly available, we have used a REDCap function called "Dashboard" that permits us to create an URL for each of the PDFs. Bright By Text (https://brightbytext.org/) is commercially available—when signing up, participants provide due date, zip code, language preference (English or Spanish) and phone number to the site. Research surveys will be sent from REDCap for all participants.

Regarding the study title: The CTSC funding submission long title, "A proposed randomized clinical trial of the effectiveness of a new breastfeeding-supportive texting program designed specifically for African-American/Black expectant women, as compared to a national maternal health texting program, on rates of exclusive breastfeeding at 2 months" has been added to both the Protocol and the Supplemental form. Due to the complexity and length of the formal title, we are requesting to retain the shorter title, "TOPS – Texting to Promote Breastfeeding," as the header in the informed consent. The reason for this request is that the population of interest may have low health literacy and may have negative perceptions of very academic descriptors; the study is the same and is described equally by both the short and long titles.

Community-Based Participatory Research – NA

International information – NA

References

- 1. American Academy of Pediatrics Section on Breastfeeding. Breastfeeding and the Use of Human Milk [Policy Statement]. Pediatr 2012; 129: e827–e841. doi:10.1542/peds.2011-3552

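### The enrollment knowledge quiz appears to show both arms the answers to a quiz repeated at 2 months, which would weaken the exploratory Hypothesis 3 knowledge contrast by an unknown amount

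*Combined protocol and SAP*

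**What the plan says.** The Study Timeline table gives the enrollment surveys. One is a knowledge quiz of four "questions – answers follow". The two-month row lists the "Breastfeeding Knowledge Quiz" again, with no alternate form and no different item count.

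Under Outcome Measures, Aim #3, the two administrations are used as a pair: "By measuring breastfeeding knowledge at enrollment and again at 2 months we will assess for change in knowledge", and to relate knowledge to the main breastfeeding outcome. Hypothesis 3 sets the between-arm expectation, with the Team2BF group "demonstrating a significantly greater increase in these domains with time as compared to the Bright By Text group". Aim 3 is labelled exploratory.

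Under Additional Information, "Research surveys will be sent from REDCap for all participants", and no arm-specific version is described. The paragraph on management of surveys allows the enrollment surveys to be completed on paper when a phone cannot read the QR codes. The Data Analysis Plan gives no analysis of the knowledge score, no scoring rule, and no handling of retest or ceiling effects.

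**The concern.** A pre-post quiz measures what an intervention taught only if nothing else in the study teaches the same items in between. Here the measurement itself seems to do so. The comparator was chosen because breastfeeding is not its focus (Background), and it carries only 8 breastfeeding messages from the prenatal period to 4 months postpartum (Study Procedures). If the comparator arm is also given the quiz answers, part of its gain comes from the answer key. In the Team2BF arm, an item already learned from the answers can no longer be gained from the texts.

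Two readings are at stake. The between-arm difference in knowledge would be smaller than the difference the texts alone would produce, so a null result could mean that the texts taught little or that the answers had already taught it. And a rise from enrollment to 2 months within either arm would mix texting with answer feedback.

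**Working it through.** The plan states no score, standard deviation, effect size or power for the quiz, so there is no figure to reproduce. The check has three steps.

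**1. Are the answers shown to participants, and are the items the same?** The timeline table speaks to the participant (the enrollment row refers to your name and age), so the note on answers most naturally describes what she sees. The shared quiz name and the planned change analysis imply the same items at both times. Neither point is stated outright.

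**2. How long is the gap between quizzes?** Texting runs "from time of enrollment (24-34 weeks) through one year postnatally", and "Mother participants who deliver prior to 36 weeks (35 and 6/7 weeks or before) will be exited from the study". Two months is taken as 8.7 weeks.

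- Shortest: enrolled at 34 weeks, delivered at 36: (36 − 34) + 8.7 = 10.7 weeks.
- Longest: enrolled at 24 weeks, delivered at an assumed 40: (40 − 24) + 8.7 = 24.7 weeks.

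The eligibility table sets no lower gestational limit, so an enrollment before 24 weeks would lengthen the gap.

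**3. What would retained answers do to the contrast?** All four inputs below are assumptions; the documents give none of them.

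- p: share of items correct at enrollment
- r: share of items wrong at enrollment that are learned from the answers and still known at 2 months
- c, g: share of the remaining unknown items learned from the texts in Bright By Text and in Team2BF

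With one point per item (also assumed), the 2-month means are 4[1 − (1 − p)(1 − r)(1 − c)] and 4[1 − (1 − p)(1 − r)(1 − g)]. The between-arm difference is

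4(1 − p)(1 − r)(g − c).

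The enrollment score is taken before the answers and is balanced by randomization in expectation, so this is also the expected difference in change. Whatever p, c and g are, it is (1 − r) times its value without answers.

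Illustration with p = 0.65, c = 0.10, g = 0.50. Without answers: 4 × 0.35 × 0.40 = 0.56 points. With r = 0.5: 0.56 × 0.5 = 0.28 points. Power is simulated with a two-sided Welch t-test at alpha 0.05, 4,000 replicates, independent items, and 36 per arm (the evaluable number in the Data Analysis Plan).

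| r | Mean, Bright By Text | Mean, Team2BF | Difference | At 4 of 4, Bright By Text | At 4 of 4, Team2BF | Power |
|---|---|---|---|---|---|---|
| 0 | 2.74 | 3.30 | 0.56 | 22% | 46% | 79% |
| 0.25 | 3.06 | 3.48 | 0.42 | 34% | 57% | 63% |
| 0.50 | 3.37 | 3.65 | 0.28 | 50% | 69% | 43% |
| 0.75 | 3.69 | 3.83 | 0.14 | 72% | 84% | 22% |

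For p from 0.50 to 0.80, the difference is 0.80 down to 0.32 points at r = 0 (power about 95% to 50%) and 0.40 down to 0.16 at r = 0.5 (about 60% to 25%).

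For gains within an arm, the enrollment mean at p = 0.65 is 4 × 0.65 = 2.60. The comparator gain is 2.74 − 2.60 = 0.14 points without answers and 3.37 − 2.60 = 0.77 points at r = 0.5, with identical texts.

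**The case against.** The strongest reply is that the central fact rests on two words in a table cell. No quiz, survey screen or answer sheet is in the documents; the note could mean that an answer key follows in a survey document, and nothing says when answers are delivered. This stands as a reason to ask the sponsor. It does not remove the point, because the table is worded for the participant and nothing elsewhere says that answers are withheld.

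Second, a reader might infer that the timeline demonstrates a ceiling. It does not. A ceiling depends on enrollment scores and on retention, and neither is given. After roughly 11 to 25 weeks, retention from a single exposure may be small; at r = 0.10 the illustrative difference would fall only from 0.56 to 0.56 × 0.9 = 0.50 points. The 25% to 75% range restates an assumed r and is not an estimate.

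Third, a reader might infer that the comparison is biased in favour of one arm, or that a null result would be uninterpretable. Neither follows. Both arms get the same surveys, so the randomized contrast still estimates what Team2BF adds beyond common feedback. A positive result would remain credible, and a null would be possibly attenuated, not meaningless.

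Finally, the aim is exploratory, knowledge is one of three domains in it, and no answer key is mentioned for self-efficacy or social support. This is correct and limits the severity.

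**Conclusion.** The point holds for direction only. If participants see the answers at enrollment and the 2-month items are the same, any retained answers move the Hypothesis 3 knowledge contrast toward zero, by about the retained share r, and gains within an arm cannot be attributed to texting alone. This assumes that answers and texts act independently, so that seeing the answers does not change how much a woman then learns from the texts.

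The actual size cannot be determined from the documents. The scores and power figures above show how the effect scales; they do not predict what this trial will see. The point does not bear on the measurement of exclusive breastfeeding at 2 months, which has its own survey. It is a cheap improvement of low severity.

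**What to change.** State in the protocol whether participants are shown the quiz answers, when, and whether the 2-month items are identical to those at enrollment.

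If answers are shown, give the enrollment quiz without them, in both the electronic and the paper version, and send the answers to both arms once the 2-month quiz is submitted. This takes an edit to the enrollment survey and one later message. The downside is that women receive the answers later.

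If some women have already been shown the answers, say so. Report 2-month scores by arm adjusted for the enrollment score, with the share at the maximum score in each arm, and describe a null knowledge result as possibly attenuated. This discloses the lost contrast but does not recover it.

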In this research, we follow up on prior work that assessed the feasibility and acceptability and content of a culturally-tuned Breastfeeding-supportive Text Messaging Library intended for AA/B women. That work (TEAM2BF, STUDY20221270) demonstrated that expectant and delivered AA/B women found the text messaging process and content acceptable and helpful. None stopped any or all of the messaging, and approximately 6 messages were revised as recommended by participants. In this current study we aim to obtain preliminary efficacy data by comparing this texting library aimed at promoting breastfeeding to a professionally endorsed national maternal child health texting program, Bright By Text, whose focus is not breastfeeding. By comparing the TEAM2BF texting program to Bright By Text, we can compare whether message content impacts breastfeeding initiation and exclusivity at 2 months. The study design is equitable for participants in that both programs use a similar approach (texting), both are designed to be accessible to minoritized women of low socioeconomic status, and the comparator (Bright By Text) has demonstrated benefits.[16] This study aims to address identified gaps in breastfeeding support for AA/B women that we hope can ultimately reduce racial inequities in breastfeeding rates.

Inclusion and Exclusion Criteria

| | | Inclusion Criteria - mothers |
|--|--|---|
| 1. Expectant women initiating obstetrical care <34 weeks or at any | | Expectant women initiating obstetrical care <34 weeks or at any prenatal visit up |
| | | to 34 weeks gestation |

| 2. | Daily access to a mobile phone with text message capabilities, |
|----|--|
| 3. | 18 years or older (i.e., adult), |
| 4. | Self-identify as African-American/Black, |
| 5. | English speaking, and |
| 6. | Infant feeding plan of "might or will breastfeed". |
| 7. | Receive care at Ahuja Midtown or MAC1200 |

| | Exclusion Criteria |
|--|--------------------------------------|
| 1. | Minors |
| 2. Committed to feeding formula only to their infant | |
| 3. | No mobile phone with text capability |

| | Inclusion Criteria - infants |
|----|--------------------------------|
| 1. | Infant of maternal participant |

| | Exclusion Criteria -infants | |
|----|---------------------------------------|--|
| 1. | 1. Not infant of maternal participant | |

Number of Research Participants

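### The Aim 1 continuation criterion is worded as receipt of messages, but the plan supplies only opt-out information for it, so silent non-use counts as continuing

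*Combined protocol and SAP*

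**What the plan says.** All references are to the combined protocol and SAP.

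- **Outcome Measures, Aim #1.** The reasoning and the rule are given in one sentence: "Receipt of messages measures acceptability because participants can easily end messaging; if at least 90% of Team2BF participants continue receipt this will indicate acceptability". The next sentence adds a 4-point helpfulness item and a referral item, described as enhancing this outcome. No time point is given.
- **Study Hypotheses, item 1.** Acceptability is defined by three targets together: more than 90% continuation, more than 75% giving the top helpfulness score, and more than 75% endorsing referral of friends and family.
- **Study Procedures, Intervention.** For Team2BF: "We are not able to collect user interactions with the SMS system (were texts read or not, was message link clicked or not". For Bright By Text the vendor can collect such data, but "there is no plan to collect this information for the research and no ability for the study team to receive or access it". Team2BF participants can stop all texts or ask for fewer.
- **Study Procedures, later items.** Survey non-responders get one reminder text and up to three calls to check for technical difficulties. Source records are the surveys and the medical record.
- **Background.** On the earlier Team2BF study: "None stopped any or all of the messaging".

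**The concern.** Receipt and not opting out are different quantities. The rule treats them as one because stopping is easy. Ignoring, muting or blocking a text is easier still, and a lapsed number requires no action at all. None of these produces an opt-out, so each scores as continuing.

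At stake is what the 90% figure can tell the team. Aim 1 asks whether a scaled-up programme is feasible and acceptable, and the outcome section lets this figure indicate acceptability. If it cannot respond to silent non-use, a high value is weak evidence of acceptance. Without any exposure measure, the team also learns little about how much texting reached women in either arm, which is basic information for planning a larger trial.

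**Working it through.** **What the plan gives.** The 90% cut-off is a chosen value. No null rate, error rate or derivation is stated, so there is no calculation to reproduce. The denominator does reproduce from the Data Analysis Plan: 36 / (1 − 0.10) = 40 per group.

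**What is observed.** Setting the sections side by side:

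| Behaviour, Team2BF arm | Recorded under the plan? | Scored by the 90% rule as |
|---|---|---|
| Stops all texts | Yes | Not continuing |
| Asks for fewer texts | Yes | Not stated |
| Receives but does not read | No (reading and clicks cannot be collected) | Continuing |
| Blocks texts, or number lapses | No delivery record planned; calls may reveal some cases | Continuing (no rule reclassifies) |

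**Sensitivity of the rule.** Let s be the share who opt out and u the share of the rest who silently do not receive the texts (or, for a reading criterion, do not read them; one definition must be kept throughout). Both are assumptions, as the documents give no values. Women are treated as independent.

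- Measured continuation = 1 − s.
- Actual continuation = (1 − s)(1 − u).
- Threshold at n = 40: 0.90 × 40 = 36.
- Probability of passing = P(X ≥ 36), X binomial with n = 40 and the relevant proportion.

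| s | u | Measured | Actual | P(pass), rule as written | P(pass) if u were observed |
|---|---|---|---|---|---|
| 0 | 5% | 100% | 95% | 1.00 | 0.95 |
| 0 | 10% | 100% | 90% | 1.00 | 0.63 |
| 0 | 20% | 100% | 80% | 1.00 | 0.08 |
| 0 | 30% | 100% | 70% | 1.00 | 0.003 |
| 5% | 5% | 95% | 90.2% | 0.95 | 0.65 |
| 5% | 10% | 95% | 85.5% | 0.95 | 0.29 |
| 5% | 20% | 95% | 76% | 0.95 | 0.02 |
| 5% | 30% | 95% | 66.5% | 0.95 | 0.001 |

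The rule-as-written column depends on s alone. With no opt-outs, 40/40 has an exact 95% interval of 91% to 100% whatever u is.

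**The two threshold wordings.** At n = 40, 'at least 90%' needs 36 and 'more than 90%' needs 37 (36/40 is exactly 90%). At a true rate of 90% the pass probabilities are 0.63 and 0.42.

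**Why non-responders cannot simply be scored as failures.** Suppose the planned 10% attrition is non-response at 2 months, nobody opts out and every responder confirms receipt. The figure is then 36/40 = 90%, which misses the more-than-90% wording and only just meets the other. One more loss gives 35/40 = 87.5%, which misses both. Such a criterion would mostly measure survey retention.

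**The case against.** The strongest reply is that continuation does not stand alone. The hypothesis joins it to helpfulness and referral, and a woman who ignores the texts is an unlikely source of top helpfulness scores. The plan also discloses that reading cannot be tracked. It collects reasons for unsubscribing, invites interviews at any unsubscribe and at 6 months, runs Maternal Satisfaction surveys at 2, 3 and 6 months, and calls survey non-responders. A lapsed number has several chances to come to light.

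Much of this stands. It limits the point to the continuation component but does not remove it: only survey responders answer the two companion items, their denominators are not stated, the outcome section makes them enhancements, and no rule carries what the calls or surveys find into the 90% figure.

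Four stronger readings are tempting, and the documents do not support them:

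- *The whole acceptability verdict can be met by silence.* Not under the three-part hypothesis.
- *Delivery cannot be observed.* Only reading and clicks are ruled out. That delivery goes unrecorded is inferred from the source-record list and the absence of any delivery plan; the system may be able to report it.
- *The measure was already at its ceiling in the earlier study.* No one stopped, but no sample size or follow-up length is given.
- *Women in one CenteringPregnancy group are split between arms, so cross-exposure undermines Aim 2.* The text says only that blocks are by group, which does not settle whether groups are split or allocated whole. Interpreting a null Aim 2 result is in any case a separate matter.

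**Conclusion.** The point holds for the continuation component of Aim 1. As planned it measures absence of opt-out, and it does not respond to silent non-use of any size. How far this matters depends on the silent share, which is unknown. With no opt-outs, the chance of passing a criterion that observed silent non-use falls from 0.95 to 0.003 as that share goes from 5% to 30%, while the rule as written stays at 1.00. These figures assume 40 independent women and a threshold of 36. They describe the component only, since helpfulness and referral give partial protection.

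The component also lacks a time point (texting runs to one year, while the Data Analysis Plan puts end of study at 6 months), carries two threshold wordings, and does not say how a request for fewer texts, or exit for delivery before 36 weeks, is counted. The primary breastfeeding endpoint is not affected. This is a modest but worthwhile correction.

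**What to change.** 1. Rename the component 'did not opt out'. Judge it at one fixed time point, for example 2 months, with one threshold wording in Study Hypotheses and Outcome Measures. State how requests for fewer texts and early-delivery exits are counted.
2. Add two short items to the existing 2-month survey in both arms: whether the woman still receives her assigned texts and roughly how many she reads (most, some, few, none); and whether she has received or been shown texts from the other programme.
3. Report self-reported receipt and reading beside the opt-out figure, both among responders and among all randomised Team2BF women with non-response shown as its own category. Report receipt and cross-exposure by arm. If the texting system provides delivery status, report that too.
4. Base the acceptability conclusion on opt-out, receipt and reading, helpfulness and referral together. Do not score every survey non-responder as not continuing within the 90% rule.

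Cost: two items in a survey already planned at 15 minutes, plus protocol wording. The downsides are self-report error and a possibly less favourable acceptability figure.
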